4.3.3 Simulation

When possible, the simulation CT will be used as the baseline study for response assessment. Therefore, the simulation CT borders should generally be extended to include all known areas of extracranial disease. During radiotherapy simulation, customized immobilization devices will be formed for each patient. For targets in thorax or upper abdomen, 4-dimensional CT (4 D CT) will be acquired in the treatment position.

Acquisition of a PET CT in the treatment position is encouraged but not required.

4.3.4 Treatment planning

The treating physician will contour the GTV. No explicit expansion for microscopic extension will be added to form the clinical target volume (CTV), i.e., CTV = GTV. The only exception is tumors in the spine, which will have a custom CTV margin

added as per International Spine Radiosurgery Consortium guidelines, because of the high risk of failure when GTV alone is treated [Cox 2012]. For treatments in the chest and upper abdomen, breathing induced tumor motion will be assessed using the 4DCT data and managed by deep inspiration breath hold, respiratory gating, dynamic tumor tracking, or motion inclusive technique, and the internal target volume (ITV) will be designed accordingly. Up to a 7mm setup margin will be added to the ITV (or GTV for treatments outside of the chest/upper abdomen) to form the final planning target volume (PTV). It is acceptable to reduce the PTV margin in the vicinity of critical normal structures such as spinal cord, bowel, or esophagus.

The treatment plan will be generally be normalized such that at least 95% of each PTV is covered by the prescription dose. It is acceptable to cover less than 95% of the PTV with prescription dose in cases of PTV overlap with critical normal structures. An inhomogeneous dose distribution (i.e., maximum point dose ~120-150% of prescription dose) is acceptable as long as the hot spot is centered in the GTV and normal tissue constraints are met.

Treatment will be delivered using 6-15 MV photons using a linear accelerator with daily kilovoltage (kV) X-ray imaging and/or daily cone beam CT for anatomy based matching. Intensity modulated radiation therapy (IMRT), particularly volumetric modulated arc therapy (VMAT), is highly encouraged. 3D conformal therapy can also be used. If 3D conformal therapy is used, it may be necessary to treat two sets of fields daily: one set that covers the full tumor, and another that covers only the part of the tumor not overlapping critical normal structures. For example, for a tumor abutting the spinal cord, the periphery of the tumor could receive a dose of 30 Gy in 10 fractions while the central part of the tumor receives a total of 40 Gy in 10 fractions using a separate set of fields that avoid the spinal cord.

Highly conformal treatment will be given. The ratio of the volume receiving greater than or equal to the prescription dose to the PTV volume should ideally be < 1.2.

4.3.5 Critical structures

Because of the variety of fractionation schedules and disease sites within the body to be treated, absolute normal tissue dose requirements are not specified in this protocol. Stanford institutional guidelines on normal tissue doses exist for each disease site and will be used.

Dose constraints will be based on the individual radiation plans for the 1-4 treated lesions. A plan sum should also be generated if multiple lesions are treated, to make sure that additive organ doses are not excessive.

When a small part of a critical structure overlaps the PTV, it is acceptable for the dose to 0.03 mL of the critical structure to be up to 110% of prescription dose within the overlap region.

4.3.6 R.T. Quality Assurance Review

Every radiation plan will be prospectively reviewed by the protocol investigators.

4.3.7 Radiation therapy adverse events

Potential radiation therapy adverse events depend on the treated location. We expect that most treated lesions will be in the thorax. Therefore, acute toxicity could include esophagitis causing pain with swallowing, fatigue, skin reaction, or cough.

Subacute/late toxicity could include radiation pneumonitis, lung fibrosis, chest wall fracture/rib pain, hemoptysis, large airway necrosis, heart failure, pericarditis, esophageal stricture.

Symptomatic radiation pneumonitis should be treated with inhaled or oral steroids. Severe cases should be treated with high dose oral steroids for at least a one month taper.

For treatment of extra-thoracic disease sites, acute toxicity could include skin reaction, fatigue, nausea, vomiting, dysphagia, and mucositis. Subacute/late toxicity could include skin changes/alopecia, brachial plexopathy, stroke, myelitis, bowel obstruction/perforation/fistula, spinal compression fracture, other bone fracture, radiation-induced river disease, kidney failure, change in bowel/bladder habits, sexual dysfunction.

4.4 General Concomitant Medication and Supportive Care Guidelines

Guidelines for use of medications for treatment toxicity are listed in sections 4.2.3 and 4.3.7. Other supportive care, such as management of pain, will be as per standard Stanford Cancer Center clinical practices.

4.5 Criteria for Removal from Study

Patients will be removed from the treatment plan and switched to usual care at time of:

1. Unacceptable toxicity
2. Progression of disease
3. Patient withdrawal of consent

4.6 Alternatives

Patients are allowed to withdraw consent for study treatment at any time, and would be switched back to standard of care treatment with systemic therapy and/or radiation therapy.

5. INVESTIGATIONAL AGENT/DEVICE/PROCEDURE INFORMATION

5.1 Investigational Agent/Device/Procedure

No investigational agents or devices will be used in this study. The study tests a combination of two standard of care treatments: anti-PD-1/anti-PD-L1immunotherapy (current approved agents are nivolumab, pembrolizumab, or atezolizumab); and conformal image-guided radiation therapy.

5.2 Study agent #1: nivolumab (Opdivo)

Nivolumab is a monoclonal antibody that blocks the interaction between PD-1 and its ligands,

PD-L1 and PD-L2. This releases PD-1 pathway mediated inhibition of the immune response, including the anti-tumor immune response. It is FDA approved for treatment of metastatic NSCLC with progression on platinum-based chemotherapy or EGFR/ALK targeted therapy. For details of pharmacokinetics and toxicity data, please see the most updated package insert.

5.3 Study agent #2: pembrolizumab (Keytruda)

Pembrolizumab is a monoclonal antibody that blocks the interaction between PD-1 and its ligands, PD-L1 and PD-L2. This releases PD-1 pathway mediated inhibition of the immune response, including the anti-tumor immune response. It is FDA approved for treatment of metastatic NSCLC in patients whose tumors have $\geq 50\%$ PD-L1 expression, or have $\geq 1\%$ PD-L1 expression and progressed on prior therapy. For details of pharmacokinetics and toxicity data, please see the most updated package insert.

5.4 Study agent #3: atezolizumab (Tecentriq)

Atezolizumab is a monoclonal antibody that binds to PD-L1 and blocks its interactions with both PD-1 and B7.1 receptors. This releases inhibition of the immune response, including the anti-tumor immune response. It is FDA approved for treatment of metastatic NSCLC with progression on platinum-based chemotherapy or EGFR/ALK targeted therapy. For details of pharmacokinetics and toxicity data, please see the most updated package insert.

6. DOSE MODIFICATIONS

Typically, patients who experience toxicity from anti-PD-1/anti-PD-L1 immunotherapy do not have dose reduction. Instead, immunotherapy is continued at current dose or discontinued per the judgement of the treating medical oncologist. Since immunotherapy administration on this study is per standard of care, the decision on termination of the immunotherapy agent will be made by the treating medical oncologist.

If a patient is experiencing unacceptable toxicity from radiation therapy while radiation therapy is ongoing, radiation therapy will be discontinued.

7. ADVERSE EVENTS AND REPORTING PROCEDURES

7.1 Potential Adverse Events

See sections 4.2.3 and 4.3.7.

7.2 Adverse Event Reporting

Adverse events will be graded according to CTCAE v4.03. Baseline and follow up toxicities will be evaluated and documented either by the medical or radiation oncologist. At each follow-up study visit, required Adverse Events and any other grade 3-5 Adverse Events will be clearly noted in source documentation and listed on study specific Case Report Forms (CRFs). The Protocol Director (PD) or designee will assess each Adverse Event (AE) to determine whether it is unexpected according to the Informed Consent, Protocol Document, or Investigator's Brochure, and related to the investigation. All Serious Adverse Events (SAEs) occurring less than 6 months after the conclusion of study RT (unless patient has entered long-term follow-up phase due to disease progression/unacceptable toxicity) will be reported and tracked until resolution.

SAEs CTCAE Grade 3 and above, and all subsequent follow-up reports will be reported to the Stanford Cancer Institute Data and Safety Monitoring Committee (DSMC) using the study specific CRF regardless of the event's relatedness to the investigation. Following review by the DSMC, events meeting the IRB definition of 'Unanticipated Problem' will be reported to the IRB using eProtocol within 10 working days of DSMC review, or within 5 working days for deaths or life-threatening experiences.

8. CORRELATIVE/SPECIAL STUDIES

8.1 Analysis of plasma and core biopsy specimens for biomarker development

8.1.1 *Collection of specimens*

For patients who consent to the optional blood testing component, peripheral blood specimens will be drawn before and after radiation therapy, and optionally at follow-up visits. The first specimen will be drawn on the first day of RT (before RT), or up to 14 days before that. The second specimen will be drawn on the last day of RT (after RT), or up to 14 days after that. Also, if a patient has pre-radiation CT-guided biopsy or fiducial placement for routine clinical purposes, research cores may be obtained during that procedure. Collection of specimens is optional. Patients will elect whether they want to participate in this portion of the study on the consent form. This correlative study will be performed at Stanford University.

8.1.2 *Handling of specimens*

- a) For each blood collection, up to 50 ml will be drawn (purple/violet tubes, EDTA preserved). EDTA tubes must be stored as soon as possible between 1-6°C until processed. The samples are viable for up to 24 hours after collection if stored at proper temperature
- b) After collection, blood will be centrifuged at low RPM. The plasma will be removed and centrifuged at high RPM, then stored at -80°C. ctDNA analysis will be performed on this specimen in collaborator's labs at Stanford University. The remaining cellular material will then be stored at -80°C for later immune marker analysis.
- c) Core biopsy specimens: The core biopsy samples will be brought immediately to the pathology department for processing.

De-identified specimens may be saved for future research. If additional correlative work is proposed pending scientific advances, this may require the cooperation of other laboratories.

8.1.3 *Coding of specimens for privacy protection*

At the time of registration each patient will be given a specific confidential identification number (IDN). Specimens will be stored under the patient's IDN. The information can be shared with other investigators listed on this protocol. Study data will be maintained in password protected computer files (protected online database). Only research personnel will have access to this information.

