4.2 Drug therapy

4.2.1 Immunotherapy administration

Patients will continue on the same anti-PD-1 or anti-PD-L1 immunotherapy that they were previously receiving. Currently available anti-PD-1/anti-PD-L1 drugs include nivolumab, generally dosed every 2 weeks or every 4 weeks, pembrolizumab, generally dosed every 3 weeks, and atezolizumab, generally dosed every 3 weeks. It is acceptable to give cytotoxic chemotherapy along with immunotherapy, but no chemotherapy can be given from 7 days before first day of protocol radiation therapy to 7 days after last day of protocol radiation therapy. For chemotherapy/immunotherapy combinations, only standard of care regimens are allowed. Currently the allowed combinations are carboplatin/pemetrexed/pembrolizumab and pemetrexed/pembrolizumab [Langer].

Laboratory monitoring for patients on immunotherapy will be performed as per standard of care. For labs required at study entry (CBC w/ diff and CMP), the medical or radiation oncologist will review and initial with date on any abnormal laboratory value/report.

As systemic therapy will be given as per standard of care, it is acceptable for immunotherapy to be given by a physician outside of Stanford ie. local oncologist, however, a Stanford physician will need to evaluate the subject at protocol specified follow up time points. Additionally, study visits may be conducted via video (i.e., MyHealth video, telehealth, telemedicine) or phone.

If there is RECIST 1.1 disease progression or unacceptable toxicity, the patient will be considered to be off of protocol therapy and will not be required to be seen at protocol specified follow up time points. After progression, it will be the decision of the treating medical oncologist whether to continue immunotherapy, switch to another therapy, or discontinue active therapy.

The treating medical oncologist may also decide to stop immunotherapy for other reasons such as an excellent sustained radiographic response to treatment. In this case, the patient should continue on the protocol follow-up schedule.

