4.3 Radiation Therapy

4.3.1 Radiation therapy overview

Radical-dose radiation therapy will be given to 1-4 extracranial lesions. Radiation therapy must be given at Stanford. The lesions to be treated are at the discretion of the treating radiation oncologist. Factors in favor of selecting a lesion include large size, progression on most recent imaging, causing symptoms, and being in a threatening location (further growth is likely to cause symptoms). A conglomerate of masses or

closely spaced masses can be considered to be one lesion.

Treatment of brain metastases is not part of protocol therapy. Brain metastases, if present, will be treated as per standard of care, generally with radiation therapy.

It is acceptable to treat the 1-4 lesions concurrently or sequentially, as long as total planned course of treatment is 10 daily sessions or less. Radiation therapy should be completed in around two weeks, though it is acceptable to extend this if necessary, for instance due to department holidays or linear accelerator downtime. Ideally, radiation therapy will start on the day of an immunotherapy infusion. However, this will not always be possible for logistical reasons. If a RT session falls on the day of an infusion, the two treatments can be given in either order.

If a lesion has previously been treated with external beam radiation therapy, it is not eligible to be treated on this study. However, it is acceptable for a radiation field to about a prior field.

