⁶ Blood drawn before first fraction of RT or any time up to 14 days before first fraction.

⁷ Blood drawn after last fraction of RT or any time up to 14 days after last fraction.

⁸ Optional

⁹ Labs collected prior to study and prior to each cycle of immunotherapy at the discretion of the treating medical oncologist.

¹⁰ After disease progression/unacceptable toxicity, vital status will be recorded every 6-12 months by chart review and/or telephone calls.

¹¹ Adverse events will be recorded until the 96-week follow-up visit. Starting with the 108-week follow-up visit, adverse events will not be recorded, and the history & physical exam, ECOG PS, and imaging studies will all be optional.

¹² Within 60 days prior to first dose of study radiation therapy

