10.4.4 Measurement Time Points

- ctDNA specimens (also see section 8.1.1): The first specimen will be drawn on the first day of RT (before RT), or up to 14 days earlier. The second specimen will be drawn on the last day of RT (after RT), or up to 14 days later.
- Radiographic response: Each post-RT restaging imaging study will be scored for RECIST 1.1 response, until best response is achieved.

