10.5.3 Measurement Time Points

- Peripheral blood flow cytometry specimens (also see section 8.1.1): The first specimen will be drawn on the first day of RT (before RT), or up to 14 days earlier. The second specimen will be drawn on the last day of RT (after RT), or up to 14 days after.
- Radiographic response: Each post-RT restaging imaging study will be scored for RECIST 1.1 response, until best response is achieved.

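### The research blood draws may be taken up to 14 days either side of RT but chemotherapy is barred for only 7, so in chemo-immunotherapy patients a compliant draw pair can span a cytotoxic dose

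*Protocol*

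**What the plan says.** The draw windows appear in four places and agree.

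- Section 8.1.1, pre-RT draw: "The first specimen will be drawn on the first day of RT (before RT), or up to 14 days before that". Calendar footnote 6 repeats it: "Blood drawn before first fraction of RT or any time up to 14 days before first fraction".
- Section 8.1.1, post-RT draw: "The second specimen will be drawn on the last day of RT (after RT), or up to 14 days after that". Calendar footnote 7 says the same: "Blood drawn after last fraction of RT or any time up to 14 days after last fraction".
- Section 10.4.4 (ctDNA) and section 10.5.3 (immune markers) carry the same 14-day limits into the two secondary outcomes: "The second specimen will be drawn on the last day of RT (after RT), or up to 14 days later" and "The second specimen will be drawn on the last day of RT (after RT), or up to 14 days after".

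Section 4.2.1 permits two pemetrexed-containing combinations with pembrolizumab, one of them with carboplatin. Its only timing limit on chemotherapy is that "no chemotherapy can be given from 7 days before first day of protocol radiation therapy to 7 days after last day" of RT.

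Sections 10.4.1 and 10.5.1 put every irradiated patient with both draws into the biomarker analyses. Section 12.2.2 plans a signed-rank test of change and a rank-sum test against response, with Cox models if feasible. None of these sections mentions chemotherapy given between the draws.

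**The concern.** Section 2.4 presents the ctDNA change as a possible early marker of response to radiation. It even suggests that a large change could prompt irradiation of further lesions. That reading needs the interval between draws to be free of other new anticancer exposure as far as the protocol can arrange it.

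The protocol already has a chemotherapy-free period around RT, but the draw windows extend 7 days beyond it on each side. A cytotoxic dose in that margin can plausibly change ctDNA and circulating immune cells, and it can also influence best RECIST response. It would then act on both sides of the planned correlation and would enter the signed-rank test of change. Part of an association credited to radiation could come from chemotherapy.

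**Working it through.** The protocol gives no figure of its own to reproduce here, so the check is calendar arithmetic.

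**Inputs.** Call the first RT day 0 and the last RT day L.

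| Item | Permitted days | Source |
|---|---|---|
| Pre-RT draw | -14 to 0 (15 days) | 8.1.1, 10.4.4, 10.5.3, footnote 6 |
| Post-RT draw | L to L+14 (15 days) | 8.1.1, 10.4.4, 10.5.3, footnote 7 |
| Chemotherapy barred | -7 to L+7 | 4.2.1 |

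Within the draw windows, chemotherapy is therefore allowed on days -14 to -8 and on days L+8 to L+14.

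**Step 1: share of permitted schedules.** A dose can fall strictly after the pre-RT draw and before RT only if that draw is on days -14 to -9. That is 6 of 15 days, so 9 of 15 are safe. On the other side, a dose can fall strictly before the post-RT draw only if that draw is on days L+9 to L+14, again 6 of 15.

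- There are 15 × 15 = 225 permitted pairs, of which 9 × 9 = 81 are safe on both sides.
- Exposed pairs: 225 - 81 = 144, and 144/225 = 64%. The result does not depend on L.
- If a dose on the draw day itself also counts, 8 of 15 days are safe on each side. Exposed pairs are then 225 - 64 = 161, or 72%.

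These are pairs in which a dose could lie between the draws, not pairs in which one does.

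**Step 2: share of chemotherapy patients.** This step needs assumptions that the protocol does not supply:

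- a 21-day chemotherapy cycle;
- the last pre-RT dose evenly spread over days -28 to -8;
- a dose that falls due inside the bar given on the first allowed day, L+8;
- draw days evenly and independently spread over their windows.

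For 10 weekday fractions (L = 11):

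- Pre-RT side: a dose on day -13 has 1 earlier permitted draw day, a dose on day -12 has 2, and so on up to 6 for day -8. The sum is 21. The probability is 21/(21 × 15) = 1/15 = 6.7%.
- Post-RT side: every next dose falls due on days -7 to 13, inside the bar (which ends on day 18), so it moves to day 19 = L+8. The post-RT draw follows it on 6 of 15 days, or 40%.
- At least one dose between draws: 1 - (14/15)(9/15) = 44%.
- A dose on both sides: (1/15)(6/15) = 2.7%.

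For a 3-day course (L = 2), some next doses fall due after the bar ends. Enumerating the same rules gives 38% on the post-RT side, 43% for at least one dose, and 2.0% for a dose on both sides.

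**Step 3: number of patients.** Section 12.2.2 reports 42 treated patients. The share on chemotherapy is not stated, so 10-30% is assumed: 4.2 to 12.6 patients. Multiplying by 0.44 gives 1.8 to 5.5, or about 2-6 patients, before loss to non-consent because the draws are optional.

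**Step 4: after the change.** With draws limited to days -7 to 0 and L to L+7, no permitted chemotherapy day lies between them, so the count of exposed pairs is 0.

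**The case against.** The strongest reply concerns size and purpose, and much of it stands.

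- **Draw timing.** The study calendar places the draws under the first and last RT day, and RT must be given on site. Draws on those days lie inside the chemotherapy bar and carry no exposure. If most were taken then, the share falls well below 43-44%. This stands.
- **Few patients.** Section 2.2 expects most patients to be on second-line or later immunotherapy, the draws are optional, and the chemotherapy share is unknown. This stands.
- **Late in the trial.** Section 12.2.2 reports 42 patients treated, against a total of at least 43 in section 12.3. New draw windows would govern few further patients, so the handling of collected pairs matters more. This stands. That handling might be thought a matter for the statistical analysis plan. But the protocol itself fixes the draw windows, and it defines the analysis set as everyone with both draws.
- **The endpoints are correlations, not causal estimates.** This is true of their titles, and section 2.4 also speaks of response to the combination. But the same section names early response to radiation as the aim of the ctDNA study, so the reading at risk is the protocol's own.

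Three stronger readings are tempting, and the documents do not support them.

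- A reader might take 7 unprotected days out of 14 and infer that half of each window, and so three quarters of pairs, is contaminated. The day count gives 64%, or 72% with same-day dosing, and both describe schedules.
- A reader might infer that aligned windows would isolate the RT effect. They would not. Immunotherapy continues throughout, and RT ideally starts on an infusion day.
- A reader might infer a similar fault from the same-day rule in section 4.3.1, "If a RT session falls on the day of an infusion, the two treatments can be given in either order". Nothing in the protocol shows that infusion order shifts these markers, and patients have already had at least four weeks of immunotherapy. A rule on that order would be a preference, not a correction.

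**Conclusion.** The mismatch is real and follows directly from the protocol's own windows. A fully compliant draw pair in a chemo-immunotherapy patient can include a cytotoxic dose, and the stated analysis set and tests treat that pair like any other.

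The 64% of permitted schedules is exact. The 43-44% of chemotherapy patients and the count of about 2-6 patients rest on an assumed 21-day cycle, evenly spread draw days and an assumed 10-30% chemotherapy share. Exposure is mainly on the post-RT side, and a pair spanning a dose on both sides of RT is rare (under 3% on these assumptions).

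The consequence is limited to the interpretation of secondary outcomes 3 and 4. With at most 42 pairs so far, a handful of affected ones could still matter there. The primary endpoint, toxicity and survival are untouched.

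**What to change.** 1. **Pairs already collected (the main step).** Flag every pair with chemotherapy between the two draws. Report the ctDNA-ratio and immune-marker analyses, both change and correlation with response, with and without those pairs. Base any statement about response to radiation on the chemotherapy-free pairs.
2. **Any further patients on chemotherapy.** In sections 8.1.1, 10.4.4 and 10.5.3 and footnotes 6 and 7, limit the pre-RT research draw to the first RT day or up to 7 days before it, and the post-RT draw to the last RT day or up to 7 days after it. Keep the 14-day windows for patients on immunotherapy alone.

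No change to the timing of chemotherapy, immunotherapy or RT is proposed.

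The cost is wording and one extra data flag, with no added visit or tube. A few chemotherapy patients may miss the narrower window or drop out of one of the two analyses.
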